The assessment will be performed at Visit 1 and Visit 5 *in the main phase, the Assessment&Dispensing Visits in the extension phase, EoT Visit and optionally at unscheduled visits. It is performed according to practice of the local laboratory and includes:*

2.29 8.2.6 Biochemistry

The assessment will be performed at Visit 1 and Visit 5 *in the main phase, the Assessment&Dispensing Visits in the extension phase, EoT Visit and optionally at unscheduled visits. It is performed according to practice of the central laboratory and includes:*

2.30 8.2.7.2 Local Laboratory Test

Assessments of haematology, FVIII trough levels and CD4⁺ T-cell count (if applicable) will be done at the local laboratory* as per standard of practice at the participating site. Laboratory results from the local laboratory will be recorded in the eCRF.

**in Russia and Hong Kong, CD4⁺ T-cell count is done centrally
not applicable for Serbia*

Clinically significant findings must be recorded as concomitant illness (blood samples during visit 1) or as an Adverse Event (blood samples taken *during the course of the trial. at visit 2-5, unscheduled visits and potential follow up visits*)

2.31 8.2.7.3 Central Laboratory Tests

A central laboratory will coordinate analysis and report of all laboratory safety tests related to biochemistry, viral antibody assessments (except CD4+ T-cell count), FVIII inhibitor, FVIII activity and *genotyping tests* performed in this trial. Laboratory data from the central laboratory will be reported to Novo Nordisk electronically, and in a manner that anonymity of patients will be maintained.

2.32 8.2.7.4 Blood Sampling Volume

Blood samples for laboratory analysis of efficacy, safety and other parameters will be drawn as described for the individual visits. The total volume of blood drawn during the trial will be approximately 2040- 5065 mL per patient (the higher range is for patient in inhibitor treatment

and/or for patient, who stay in the trial for a longer duration of time). According to the European regulatory guidelines (Directive 2001/20/EC)^{2,19} the recommended blood volume collected from the patient for all tests should not exceed 1% of the whole blood volume at any single time and 3% of whole blood volume in 28 days (see Appendix B). This is in accordance with Where this guideline is not applicable, local guidelines for blood sampling volumes will apply. During visits when multiple samples are taken, blood samples will be aliquoted to meet above mentioned requirements. Instructions will be provided in the Laboratory Manual and in Appendix B.

2.33 8.2.8 Physical Examination

Physical examination should be performed at Visits 1-5 and at EoT (additional examinations can be performed as appropriate) according to practice at the participating clinic including assessments of the following:

2.34 8.2.9 Vital Signs

Vital signs will be assessed at Visit 1 and Visit 5 and at EoT (additional assessments can be performed as needed) and includes:

- Body temperature (assessed by measuring inner ear temperature or using an oral digital thermometer)
- Respiratory rate (resp./min.)
- ~~Pulse: preferably supine~~
- ~~Blood pressure (BP): preferably supine~~

~~BP (systolic and diastolic) and pulse rate will be measured according to local practice at the clinic; preferably after the patient has rested comfortably for at least 3 minutes.~~

Any changes in the vital signs between the two visits which fulfil the criteria of an Adverse Event must be recorded as such, see Section 12.1.

2.35 8.3.1 Bleeds

During the entire trial period all bleeds ~~treated with turoctocog alfa~~ will be entered in either the eCRF or in the patient's diary. For ~~mild/moderate~~ bleeds *treated at home*, the patient or caregiver must fill in the diary and during visits the diary data will be transcribed into the eCRF by trial site personnel. ~~For severe bleeds (see definition in Section (8.3.1.1) the Investigator, or designated site staff, must be contacted without delay to prescribe the appropriate treatment and any follow-up procedures. It is recommended that these direct instructions are followed by, or given at, an unscheduled visit to the clinic. Documentation about the severe bleeds treated at the clinic should be entered in the medical records and eCRF by the trial personnel.~~

2.36 8.4.1 FVIII genotype testing (not applicable to Brazil)

At Visit 1 ~~2~~, all patients/parents/legally authorized representative (LAR) will be asked about documentation of previous FVIII genotype tests. If not available or if it needs to be re-tested FVIII genotype testing will be offered as allowed by local law. The blood sample should be taken at Visit 3, 4 or an unscheduled Visit. *The FVIII genotype analysis is performed at the laboratory in Bonn, Germany.* Investigator, parent(s) or LAR have the right to refuse to provide patient's FVIII genotype documentation or to refuse genotyping. This will not stop the patient to continue participation in the remainder of the ~~study~~ trial.

2.37 8.4.2 Viral Antibody Information

At Visit 1 *and at EoT* status of the following viral infections are assessed.

2.38 8.4.4 Body Measurements

Weight and height will be measured at Visits 1, 5 and EoT. For Visits 2-4 *and for the Assessment&Dispensing Visits in the extension part* only weight is measured.

2.39 8.4.5 Diaries

Diaries will be dispensed *and reviewed at all visits 2-4, except Visits 1, 2 and EoT.* The following data will be collected.

2.40 8.4.7 HE and PRO data

The questionnaire is to be filled in at Visits ~~1~~, 3 *and 5 in the main phase, annually in the extension phase and at EoT Visit* preferably before any other trial related procedures.

2.41 9.4 Dispensing and Drug Accountability of Trial Products

•No trial product(s) should be dispensed to any person not enroled in the *trial (excluding parents/LAR)*

Trial product will be dispensed at the visits depicted in the flow chart, see Table 2-1 and 2-2. The patient is required to return both used and unused vials at the next visit to the clinic or at the End of Trial Visit, as appropriate.

2.42 14 Monitoring Procedures

During the course of the trial, the Monitor will visit the trial site to ensure that the protocol has been adhered to, that all issues have been recorded, to perform source data verification and to monitor

drug accountability. The visit intervals will depend on the outcome of the remote monitoring of the eCRFs, the trial site's recruitment rate and the compliance of the trial site to the protocol and GCP, *but The intervals between visits must not exceed 8 weeks when there are patients ongoing in the trial at the site. When there are no trial active patients at the sites, intervals between visits must not exceed 12 weeks.*

2.43 18.2.2 Primary Endpoint(s)

- Incidence rate of inhibitors defined as inhibitor titres ≥ 0.6 Bethesda units/mL *for the main phase of the trial*

The incidence rate of inhibitors will be calculated and a 1-sided 97.5% upper confidence limit will be provided based on an exact calculation for a binomial distribution. For the calculation of the incidence rate the numerator will include *number of all patients with inhibitors* while the denominator will include *number of all patients with confirmed inhibitors during the main phase of trial or completed the main phase without confirmed minimum of 50 ED plus any patients with less than 50 ED but with inhibitors*.

2.44 18.2.4 Supportive Secondary Endpoints

All the below efficacy endpoints will be evaluated for the main phase of trial, for the extension phase of trial, and for the combined main and extension phases. Sensitivity analyses will be made only including patients who do not develop inhibitors during the main phase of the trial and during the extension phase of the trial. For patients that develop inhibitors only the time period until the last negative inhibitor result is considered for the efficacy endpoints below. Sensitivity analyses will be made only including patients who do not develop inhibitors. Further, tables will be made including only inhibitor patients. For these patients the relevant time period is the time period after positive inhibitor test.

Secondary Efficacy Endpoints

- Annualized bleeding rate during bleeding prevention period with turoctocog alfa

For this endpoint patients who develop inhibitors will only be included if they have been treated *with at least two doses of trial product for minimum 1 month* before the first positive inhibitor test. The reason to exclude these patients from the calculations is *that if the treatment period is too short, that the information from the treatment with one dose is too small and the uncertainty introduced on the estimated annualized bleeding rate will be relatively large.*

Separate reports and listings will be made for the above efficacy endpoints for patients developing inhibitors. Data used in these reports and listings will include data from the first time patient is confirmed with inhibitors until the end of the main phase of trial as well as until the end of trial. Furthermore, each of these reports will also be generated for different method for management of patients with inhibitors.

Secondary Safety Endpoints

- *Incidence rate of inhibitors defined as inhibitor titres ≥ 0.6 Bethesda units/mL for the extension part of trial and the combined main and extension phases of the trial.*

The incidence rate of inhibitors will be calculated and analyzed in the similar way as the primary endpoint.

Furthermore, Kaplan Meyer plots and the additional analyses outlined in Section 18.2.2 for the primary endpoint will be generated using data from the extension phase and the combined main and extension phases of the trial.

- *Frequency of AEs adverse events and SAEs serious adverse events*

AEs and SAEs will be analyzed for the main phase of the trial and the combined main and extension phases.

Separate reports and listings will be made for AEs and SAEs for patients developing inhibitors. Data used in these reports and listings will include data from the first time patient is confirmed with inhibitors until the end of the main phase of trial as well as until the end of trial.

The incidence rate of clinically relevant inhibitors and high-titre inhibitors will be evaluated for the main phase of trial, for the extension phase of trial, and for the combined main and extension phases.

All additional safety parameters such as laboratory parameters and physical examinations will be listed and summarized by visit for all patients for the main phase of trial, for the extension phase of trial, and for the combined main and extension phases

Separate reports and listings will be made for the above safety endpoints for patients developing inhibitors. Data used in these reports and listings will include data from the first time patient is confirmed with inhibitors until the end of the main phase of trial as well as until the end of trial.

2.45 18.6 Health Economics and Patient Reported Outcomes

Health economic data will be collected in the eCRF in connection with severe bleeds. Patient reported outcomes will be collected using questionnaires at Visits 3 and 5 *in the main phase, and annually during the extension phase.*

2.46 23 Responsibilities

The following will be analysed at the local laboratory: haematology, FVIII trough level assessment and CD4+ T-cell (*excluding Russia*).

~~A~~Central and specialized laboratories will analyse and report all laboratory safety tests related to biochemistry, viral antibody assessments, FVIII activity, FVIII inhibitor assessments and *potential genotyping* performed in this trial.

2.47 27 References

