Primary Endpoint

- Incidence rate of FVIII inhibitors (≥ 0.6 BU/mL) will be evaluated for the main phase of the trial

Secondary Endpoint(s)

The secondary endpoints will be evaluated for the main phase of trial, for the extension phase of trial, and for the combined main and extension phases..

Safety Endpoints:

- ---
- Incidence rate of FVIII inhibitors (≥ 0.6 BU/mL).

2.7 5.1 Type of Trial

The trial comprises 5 planned visits consists of two phases i.e. main and extension, respectively. In the main phase the patients will attend a screening visit (Visit 1) in order to assess their eligibility. At Visit 2 eligible patient will receive their first dose, if applicable, and will be scheduled to attend for 3 more visits. After Visit 5 the patients will enter the extension phase, and a rolling visit schedule will apply with 6 planned visits (including 4 dispensing visits) per year.

The *main trial phase will be completed when the aggregated number of patients will be scheduled to*, who have either received treatment with turoctocog alfa for at least 50 ED or developed inhibitors, are at least 50. ~~which~~ For the individual patient it translates into duration of the *main phase* of approximately 3-24 months depending on the dose regimens (and bleeding pattern). The duration of the extension phase may be up to 3.5 years, and the total duration of the trial is estimated to be approximately 50 months years, please see Section 7.

Patients who develop inhibitors during the trial may continue treatment with turoctocog alfa and will follow an alternative visit schedule, see Section 5.3.4. *These patients will be considered as a separate cohort and will be evaluated accordingly, please refer to Section 18.2.2.*

Details on the trial design can be found in Figure 2-1 and details on the individual visits can be found in Table 2-1 and 2-2, and in Section 8.

2.8 5.3 Treatment of Patients

Approximately 60 patients are expected to be enroled into the trial in order to have 50 *evaluable* patients ~~completing in the main phase of the trial~~ (estimated dropout rate is 15-20%). For replacement of withdrawn patients, please refer to Section 6.5.

The maximum duration of treatment of a patient from first to last turoctocog alfa administration is approximately 24-4 years month.

2.9 5.3.2 Treatment of Bleeds and Dose Adjustment

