2.39 19.1 Informed Consent Form for Trial Patients	20

2.40	19.4 Regulatory Authorities.....	21
2.41	20 Premature Termination of the Trial/Trial Site	21
2.42	23 Responsibilities	21
2.43	25 Retention of Clinical Trial Documentation.....	22
2.44	Attachment I – Global.....	22

Table of figures

	Page
Figure 12–1	17

Table of tables

	Page
Table 2–1 Visit Flow Chart main trial phase	6
Table 2–2 Visit Flow Chart trial extension phase	6

1 Introduction including rationale for the protocol amendment

The main reasons for this amendment is to re-define the duration and conditions for treatment of patients with inhibitors, restrict the number of previous exposures to blood components (to keep a homogenous PUP population), re-define the trial duration and revise the date of end of trial. In addition, the possibility to further investigate immunogenicity of turoctocog alfa e.g. non-neutralising antibodies assessment and Human Leucocyte Antigen (HLA) genotyping will be introduced. Some changes are administrative to align with updated guidelines and Novo Nordisk Standard Operation Procedures e.g. the requirement to list the participating countries has been removed.

The Patient Information and Informed Consent will be adapted accordingly.

In this protocol amendment:

- Any new text is written ***in italics***.
- Any text deleted from the protocol is written using **strike through**.
- Corrections of minor inconsistencies and ambiguities, and typographical errors will not be listed.

2 Changes

2.1 1 Summary

Trial Design

The trial consists of two phases. In the main phase, an aggregated number of at least 50 patients will receive preventive treatment with turoctocog alfa until they reach a minimum of 50 exposure days² (ED) or until they develop inhibitors. After that the patients will continue in the extension phase ~~until where at least 50 patients should achieve~~ at least 100 ED ~~has been achieved~~, which will translate into a ~~maximum~~ trial duration of up to 3.5 5 years (*including any potential inhibitor treatment*). The estimated total duration of the trial is approximately 5 7 years.

Trial Population

Approximately 60 PUP with severe (FVIII \leq 1%) haemophilia A with no history of inhibitors below 6 years of age ~~in a non-bleeding state~~ will be enrolled to allow for at least 50 patients to complete the trial

Key Inclusion Criteria

- ---

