Screening will be done at Visit 1. Visit 2 will be performed within 21 days post Visit 1, and it could be the same day as Visit 1. At Visit 2 eligible patients are enrolled and preventive treatment with investigational product (turoctocog alfa) starts if applicable (may be delayed, see section 5.3.1 start after the first two bleeds). At Visit 5, after \geq 50 ED, patients will leave the main phase of the trial and continue in the extension phase. Patients who develop inhibitors can continue with ITI treatment with an alternative visit schedule (down ward arrows). If ITI treatment is successful these patients can continue with preventive treatment according to the extension phase (upward arrows). The patients will belong to either of the groups main phase, extension phase or inhibitor cohort.

2.3 5.1 Type of Trial

The main trial phase will be completed when the aggregated number of patients, who have either received treatment with turoctocog alfa for at least 50 ED or developed inhibitors, are at least 50. In the extension phase, *at least 50* the patients will be followed until at least 100 ED has been achieved. For the individual patient it translates into duration of the main phase of approximately 3-24 months depending on the dose regimens (and bleeding pattern). The duration of the extension phase may be up to 3.5 years, and the total duration of the trial is estimated to be approximately 5-7 years, please see Section 7.

2.4 5.3 Treatment of Patients

Patients will enter a bleeding preventive regimen as described below, see Section 5.3.1. ~~Preventive treatment can be postponed until a maximum of two bleeding episodes have occurred.~~ For prevention one single bolus dose of turoctocog alfa is administered intravenously (i.v.) at each administration day. Turoctocog alfa should preferably be administered in the morning. The maximum duration of treatment of a patient from first to last turoctocog alfa administration is approximately 4 years.

2.5 5.3.1 Preventive Treatment and Dose Adjustment

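### Are the main-phase reports for inhibitor patients empty, and could an inhibitor first found at Visit 5 drop out of the primary endpoint?

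*Combined protocol and SAP*

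**What the plan says.** The plan uses *main phase* in two senses.

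- **A patient's own period.** The Summary (Amendment 7, item 2.1) has patients treated to 50 exposure days (ED) or "until they develop inhibitors. After that the patients will continue in the extension phase". The caption to Figure 2-1 adds: "The patients will belong to either of the groups main phase, extension phase or inhibitor cohort". Section 18.2.1 (Amendment 7, item 2.37) treats a patient as having finished the main phase once Visit 5 is done or an inhibitor is confirmed.
- **A trial milestone.** Section 5.1 (Amendment 7, item 2.3) says: "The main trial phase will be completed when the aggregated number of patients" with 50 ED or an inhibitor reaches at least 50.

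The rules that use the term come from the amendment introducing the extension phase, items 2.43 and 2.44.

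- The primary denominator (Section 18.2.2) is the "number of all patients with confirmed inhibitors during the main phase of trial", plus those who completed the phase without one.
- The inhibitor-patient reports of efficacy, and of safety ("Separate reports and listings will be made for the above safety endpoints for patients developing inhibitors"), use "data from the first time patient is confirmed with inhibitors until the end of the main phase of trial". The same sentence asks for a version running to the end of the trial.
- Inclusion of inhibitor patients in the bleeding rate depends on doses given "before the first positive inhibitor test".

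Section 5.1 says of inhibitor patients: "These patients will be considered as a separate cohort and will be evaluated accordingly, please refer to Section 18.2.2".

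**The concern.** Three things look wrong at first.

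1. **The report window.** If a child's main phase ends when his inhibitor develops or is confirmed, a window that opens at confirmation and closes at the end of the main phase contains nothing. The window has length only if the main phase is the 50-patient milestone, yet the incidence endpoints in the same section need the patient-level sense.
2. **The date.** One rule is anchored to the first positive test and another to confirmation, while the primary endpoint names neither. Diagnosis takes two consecutive positive central tests, and the second sample comes at an unscheduled visit, preferably within 2 weeks (Section 8.2.2.1). For a child first positive at Visit 5, that visit falls after he has left the main phase.
3. **The cross-reference.** Section 5.1 points to Section 18.2.2 for how the inhibitor cohort is evaluated, and Section 18.2.2 contains no such rule.

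Inhibitor incidence is the primary endpoint. The stakes would be a set of tables with no data, and a primary rate that depends on an unwritten choice of date.

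**Working it through.** The plan states no figure on this point, so most of the check sets the rules side by side.

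**1. Report window under each sense.** Length = end of window − confirmation date.

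- Patient sense, Section 18.2.1: the phase ends at confirmation, so the length is 0.
- Patient sense, Summary, with development dated at the first positive: the end precedes the start. For illustration, first positive at ED 13 and confirmed at ED 15 gives 13 − 15 = −2 ED.
- Milestone sense: the window runs from confirmation to the date the 50th patient qualifies. It has positive length for every child confirmed before that date.

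The reports are therefore empty only in the patient sense.

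**2. Which sense fits the sentence.** It pairs two end points, and the second, the end of the trial, is a calendar milestone. Section 18.2.1 plans two reports: a main report once at least 50 patients have completed the main phase, and an updated report once all have completed the extension. The two end points match these two data cuts. On that reading the first version has data and the second extends it.

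**3. Incidence endpoints.** These need a period that each child completes individually, and Section 18.2.1 supplies it. The milestone sense would not work here: a child past his own Visit 5 would be in both phases until the 50th patient qualified.

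**4. A Visit 5 positive confirmed later.** Inputs:

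- 50 evaluable patients (Section 5.3).
- Expected inhibitor rate 30–35% (Section 12.5.2); the lower end gives 0.30 × 50 = 15 cases.
- Exact one-sided 97.5% upper limit (Section 18.2.2), which for x cases in n is the 0.975 quantile of a beta distribution with parameters x + 1 and n − x.
- Visit 4 at 20–25 ED and Visit 5 at 50–55 ED (Table 2-1).

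Visit 5 is the only scheduled test for the last stretch of main-phase exposure. That stretch is between (50 − 25)/50 = 50.0% and (55 − 20)/55 = 63.6% of the total, so a first positive at Visit 5 is plausible.

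Under either date such a child stays in the denominator; only the numerator moves, by 1/50 = 2.0 points per case.

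| Cases moved out of the main phase | Rate | Upper limit |
|---|---|---|
| 0 | 15/50 = 30.0% | 44.6% |
| 1 | 14/50 = 28.0% | 42.5% |
| 3 | 12/50 = 24.0% | 38.2% |

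The counts of 1 and 3 are assumptions; the documents do not give the number. A moved case is not lost: it falls in the extension-phase incidence and stays in the combined-phase incidence.

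**5. Two anchors.** The first-positive anchor is an inclusion rule for the bleeding rate: at least two doses must have been given before that test. The confirmation anchor starts follow-up of the inhibitor cohort. They serve different purposes and can both stand.

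**6. Cross-reference.** The cohort reporting rule that Section 5.1 looks for is in Section 18.2.4. The pointer is a clerical slip.

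**The case for a change.** The strongest case for a change is that this is the primary endpoint, that the term does carry two senses in rules now in force, and that the later amendment of Sections 18.2.2 and 18.2.4 altered units and minor wording only. Two statisticians could follow the text and place the same child in different phases. A few sentences would prevent that at almost no cost, and before the data are seen.

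Part of this stands. The double use is real, and no sentence in Section 18.2.2 fixes the date. In that section *confirmed* may name the two-test diagnosis, or it may date it.

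The consequences are much weaker. Empty reports require the patient-level sense to be forced onto a sentence built as a pair of data cuts. One can also object that the milestone sense gives early enrollees far more main-phase time. A first child enrolled in December 2011 leaves his own main phase after 3–24 months, between March 2012 and December 2013. If the milestone fell between June 2015 and June 2016, the overlap would be 18 to 51 months. That closing date is an assumption, and the main report is planned only for Q3 2017 (Section 7). The 3–24 months is also framed by dose regimen and bleeding pattern, so it describes children on the way to 50 ED rather than inhibitor patients. Unequal follow-up at a common cut is ordinary staggered entry. Naming the main-report data cut instead would give nearly the same date, because the same 50-patient count triggers that report.

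The copy of items 2.43 and 2.44 reviewed here has also lost some deletion marks, so old and new wording run together. Close parsing of their dates is fragile.

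**Conclusion.** No change follows. What remains is a dating convention that the plan leaves unwritten and that analysts would fill sensibly. Visit 5 is a scheduled main-phase inhibitor test (Section 8.2.2), so a positive sample taken there and later confirmed is naturally a main-phase inhibitor.

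On the less natural reading the primary rate falls by 2.0 points per case at 50 patients, and the upper limit falls by about 2 points. This assumes a denominator of 50 and a base of 15 cases; the number of cases that could move is unknown and may be zero. The effect is bounded further: confirmation is preferably obtained within 2 weeks, the updated report presents main-phase data again and can take in late confirmations, the combined-phase incidence does not depend on the date, and Section 18.2.1 rules out formal hypothesis testing.

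The inhibitor-patient reports contain data when their windows are read as the two report cuts. The pointer in Section 5.1 affects no result.
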